Official Title: Safety and feasibility of Early Oral Nutrition after Endoscopic Treatment for Patients with Liver Cirrhosis: A Historical-prospective, Comparative Effectiveness study

NCT number: NCT04823780

Document date: September 1, 2020

Study protocol

The purpose of the study was to compare safety and effectiveness of different feeding time in the real-world clinical practice. Detailed history-taking and physical examination were carried out on all recruited patients and basic information were recorded including liver function by Child-Pugh's scores and MELD scores, endoscopic features. EVL was performed after confirmation of esophageal varices and cyanoacrylate was injected if gastric varices were diagnosed. Further, the octreotide was given for 24 hours postop routinely. All the therapeutic endoscopies were performed by a technically proficient gastrointestinal endoscopist. The endoscopist, data collectors and statisticians were blinded to the follow-up dietary intervention tasks.

Eligible patients in the EN group were required to fast for 4 hours following endoscopic treatment and peptisorb produced by Milupa Nutricia GmbH was used for enteral nutrition at the beginning. The initial recommended dose of peptisorb is 60 g dissolved in 250ml water, which can provide 250 kcal energy (protein 9.8 g, fat 2.45 g, carbohydrate 46.5 g). Transition to soft diet such as chicken custard could be carried out after 2 to 3 times of giving peptisorb emulsion if there were no adverse reactions. Further, it is recommended that the diet of patients should obey the principle of multiple-meal-with-small-amount-for-each and the daily meals could up to between 4 and 5 times. The time and amount of diet was recorded specifically and the total energy intake through enteral nutrition were calculated. Extra energies were supplemented by parenteral nutrition. All patients required fasting for at least 48 hours in the control group and parenteral nutrition was provided through intravenous infusion, then transit gradually from liquid diet to soft diet. All nutritional supports were provided based on the standard recommended by ESPEN guideline on clinical nutrition in liver disease that calorie requirement for $30 \sim 35 \text{ kcal} \cdot \text{kg}^{-1} \cdot \text{d}^{-1}$.

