In addition, the prospectively enrolled patients in interventional group were divided into three subgroups according to dietary time. The early enteral nutrition (EEN) in the current study was defined as starting enteral nutrition between 4 and 12 hours after endoscopic therapy and delayed enteral nutrition (DEN) was defined as between 12 and 48 hours. The dietary time after 48 hours was defined as parenteral nutrition (PN).

Outcomes and definitions

The primary endpoint of this study was variceal re-bleeding following endoscopic treatment. The secondary endpoints were mortality whereas the adverse events during the 42-day follow-up. The days and expenses of hospitalization were also compared between the two groups in this study. Besides, inflammatory factor, serum albumin level, defecation time and the satisfaction with nutritional support of patients were also evaluated in the three subgroups.

Variceal Re-bleeding includes very early rebleeding and early rebleeding. In this study, very early rebleeding was defined as rebleeding within 5 days after endoscopic treatment whereas early rebleeding was defined as within 5 and 42 days after endoscopic treatment. Rebleeding within 48 hours was considered as failure treatment. Whatever anytime, once the rebleeding occurred, the patients would receive pharmacotherapy or endoscopic treatment again.

Satisfaction of the patients with nutritional support was assessed based on 5 - point Likert scale of very satisfied (5 points), satisfied (4 points), neither satisfied nor dissatisfied (3 points), dissatisfied (2 points) and very dissatisfied (1 point). The satisfaction rate was regarded as the proportion of very satisfied and satisfied.

Statistical analysis

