Statistical analyses were performed using statistical software IBM SPSS Statistical 26.0 (SPSS, Chicago, IL). The baseline data of control group and intervention group were matched using propensity score analysis (PSM) in a ratio fashion of 1:1 using the nearest neighbor technique. Quantitative variables conforming to normal distribution were expressed as mean \pm standard deviation ($M \pm SD$) whereas the variables not conforming to normal distribution were presented as median (interquartile range (IQR), (P25, P75)). Qualitative variables were expressed as percentages. Quantitative variables were compared using Student's *t*-test, Mann-Whitney nonparametric test or variance analysis, and χ^2 test. On the other hand the Fisher's exact tests were used to compare qualitative variables in this study. Linear regression analysis was performed to find the significant factors influencing diet time after endoscopic treatment. The analysis of outcomes between the two groups was conducted based on intention-to-treat

(ITT) and per-protocol (PP) analysis. $P < 0.05$ was considered statistically significant.

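### Does leaving the intention-to-treat and per-protocol sets undefined and unranked put the rebleeding comparison at risk?

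*Combined protocol and SAP*

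**What the plan says.** The Statistical analysis section gives one sentence on analysis sets: "The analysis of outcomes between the two groups was conducted based on intention-to-treat" and, running on, "ITT) and per-protocol (PP) analysis". Significance is set at 0.05. The same section says the two groups' baseline data were "matched using propensity score analysis (PSM) in a ratio fashion of 1:1 using the nearest neighbor technique". It does not say whether the analysis sets are formed before or after matching, what counts as adherence, or which set decides if the two disagree.

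The Study protocol section gives each group one timing rule: a 4-hour fast for the EN group, and a fast of at least 48 hours with intravenous nutrition for controls. At its end, "the prospectively enrolled patients in interventional group were divided into three subgroups according to dietary time": 4 to 12 hours, 12 to 48 hours, and a third described as "The dietary time after 48 hours was defined as parenteral nutrition (PN)". Under Outcomes and definitions, rebleeding is the primary endpoint, and "Rebleeding within 48 hours was considered as failure treatment".

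**The concern.** The third subgroup belongs to the interventional group but carries a label and a timing that resemble the control regimen. The only timing rule written for EN is the 4-hour fast, which these patients meet, so they could be called adherent. Because they are labelled PN, they could equally be called off protocol and removed from PP.

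Each choice has a cost. Keeping them as EN pulls any true difference towards zero, which is not cautious when the purpose includes safety: "The purpose of the study was to compare safety and effectiveness of different feeding time in the real-world clinical practice". Removing them selects on feeding time, which is known only after treatment. A patient who rebleeds before being fed might then be fed late and drop out of the EN group alone, taking a primary event with them. With no ranking of the two sets, the more convenient result could be put forward once the data are seen.

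**Working it through.** The plan has no figure to reproduce: it states no sample size, rate, margin or feeding split. The text comes first, then illustrations on assumed values.

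**1. What is actually open.**
- ITT: in ordinary usage patients are analysed in the group they entered. No randomisation is described, but the plan speaks of patients prospectively enrolled in the interventional group, so group of enrolment serves as the anchor. PN-labelled patients stay in EN.
- PP: no criteria are given for either group. Besides late-fed EN patients, PP could exclude controls fed before 48 hours or EN patients fed before 4 hours. It therefore cannot be assumed that PP equals ITT when late-fed patients are kept, or that exclusions fall on one group only.
- The PN label rests on feeding time alone. It does not establish that these patients followed the control regimen, and EN patients also receive parenteral supplements.

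**2. Dropping late-fed patients from PP, no true effect.** Let p be the rebleeding risk in each whole group, f the late-fed share of EN, and k the risk of late-fed patients relative to the rest of EN. The EN risk in PP is p/(1 − f + f·k).
- p = 10%, f = 10%, k = 2: 0.10/1.10 = 9.09%, a shift of −0.9 points.
- p = 10%, f = 30%, k = 2: 0.10/1.30 = 7.69%, a shift of −2.3 points.
- k = 1: no shift.
- Over p = 5% to 15%, f = 5% to 30% and k = 2 to 3, the shift runs from −0.2 to −5.6 points. Nothing in the documents says where in that range, or outside it, the trial lies.

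**3. Keeping late-fed patients in EN.** If feeding by 48 hours truly adds 5.0 points and late-fed patients have the control risk, the observed difference is (1 − f) × 5.0: 4.5 points at f = 10% and 3.5 at f = 30%. This is the usual dilution in a comparison by enrolled group.

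**4. Error rate from having two analyses.** Suppose significance in either set counted as a positive result. With no effect, 10% risk, 100 or 200 per group and f = 10% or 30%, an uncorrected two-proportion z-test gives 6.0% to 7.1%. Fisher's exact test, which the plan names, gives about 4% to 5% in the same four cells. The excess needs both the uncorrected test and an either-one-wins rule that the plan does not contain.

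**5. Would a 48-hour landmark analysis be better?** This compares patients alive and free of rebleeding at 48 hours. With 10% total risk and 40% of rebleeds assumed to fall before 48 hours, later risk is 0.06/0.96 = 6.25% in both groups, provided late feeding is unrelated to risk. If late-fed patients have twice the later risk of the others, EN without them shows 6.25%/1.1 = 5.7% (f = 10%) or 6.25%/1.3 = 4.8% (f = 30%). The imbalance returns, and the comparison omits the rebleeds within 48 hours that the plan classes as treatment failure.

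**The case for a change.** The strongest case for a change is that ordinary usage supplies no PP rule and no ranking, and that the choice can affect the result. With 200 per group and true risks of 20% if fed by 48 hours against 10% otherwise, ITT detects the harm in 73% of simulated trials and PP without the late-fed in 79% when 10% are fed late. At 30% fed late the figures are 54% and 74%, and the two sets disagree in 7% and 21% of trials respectively. The plan also intends a regression on factors influencing diet time, so feeding time is treated as depending on the patient, and exclusion by it cannot be presumed harmless. Stating the sets would cost only a few sentences.

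Part of this stands. The definitions and the ranking are absent, and a large late-fed share would make the two analyses answer visibly different questions. However, every rate behind those figures is assumed, and the route from an early rebleed to exclusion from PP is possible but not shown. The planned regression also suggests that variable feeding time was expected in practice, which makes treating late feeding as a protocol breach the less natural reading. Writing the definitions down would be good practice, but it would supply detail and not correct a rule.

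**Conclusion.** No change follows. The plan leaves PP undefined and does not rank the two sets, but it states no rule that misleads, and the comparison by enrolled group, which suits a real-world question, is reported anyway. A competent analyst fills the gap in the usual way: both sets are built on the matched cohort, ITT leads, PP supports it with feeding-time criteria stated for both groups, and a rebleed or death, or a feeding delay that follows one, is not a reason for exclusion. The opposite order would also be defensible if fixed beforehand.

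The size cannot be estimated from the documents. On assumed inputs it runs from nothing, when late-fed patients carry the same risk as the others, to several points when many are fed late and their risk is two to three times higher. This conclusion assumes that ITT is read as group of enrolment. A landmark analysis is at most an optional sensitivity analysis: it needs an untestable assumption and sets aside the earliest rebleeds.
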